A potential role for incretin-based therapy in the management of critically ill patients with hyperglycemia exists. The effect of GLP-1-based therapy via *continuous infusion* on hyperglycemia following acute brain injury has not been previously evaluated, however, few studies have evaluated its therapeutic use in other critically ill populations. Following major surgery, GLP-1 infusion (1.2 pmol/kg/min) administered to eight patients with type 2 diabetes resulted in normalization of hyperglycemia (126 mg/dL) within 150 minutes of initiation.⁵⁹ Following coronary artery bypass graft surgery, GLP-1 infusion had been demonstrated to normalize blood glucose compared to both placebo and IIT with doses of 1.5 and 3.6 pmol/kg/min, respectively.^{59,60} Other published data support that GLP-1 infusion attenuates glycemic response in severely ill patients hyperglycemic during total parenteral nutrition, enteral or intragastric feeding.^{61,62} Intravenous GLP-1 infusion has been well-tolerated in all critically ill populations evaluated with minimal adverse events reported. Hypoglycemic events were not recorded in the majority of studies.^{58,59,61,62} One episode of asymptomatic hypoglycemia (43 mg/dL) occurred with GLP-1 treatment, but resolved following temporary cessation of the infusion.

The main expected outcome of this work is to demonstrate the feasibility of exenatide infusion in the management of hyperglycemia following acute brain injury. We are proposing to evaluate this aim by utilizing continuous glucose monitoring (CGM). CGM has the potential to provide real-time measurement of systemic glucose concentrations. This allows for more intensive monitoring of glycemic variability as well as hyper- and hypoglycemic events. Schuster and colleagues reported CGM is reasonable and accurate in surgical ICU patients, many of whom had recent abdominal surgery and required use of pressors and large-volume resuscitation.⁶³ Holzinger and colleagues found that CGM reduced hypoglycemic events in critically ill patients⁶⁴ and also reported that the accuracy and reliability of CGM in critically ill patients was

not impacted by circulatory shock requiring norepinephrine therapy.⁶⁵ CGM will provide a direct representation of the overall glycemic status in order to evaluate the potential of exenatide as a treatment of hyperglycemia following acute brain injury.

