Therefore, determining the incidence of ARC in this patient population and its impact on exenatide pharmacokinetic parameters is a critical area for further study *as ARC may result in subtherapeutic concentrations of exenatide*. We are proposing to evaluate this aim by measuring serum concentrations of exenatide and directly measuring urinary creatinine clearances concurrently. This will provide a direct representation of the overall renal function along with the incidence of ARC and allow for comparison of the patient's renal function with exenatide serum concentrations.

3. *To determine the impact of exenatide infusion on cerebral extracellular glucose levels and other markers of cellular distress utilizing cerebral microdialysis in eligible critically ill patients with acute brain injury.*

Background and Rationale:

Recently both experimental and clinical studies have shown that even mild hypoglycemia may result in cerebral metabolic distress.⁷⁰⁻⁷² Overall these studies show that the brain can be acidotic even with "normal" serum glucose concentrations and this cerebral glycopenia is related to poor functional outcome.⁷² There is convincing evidence to suggest that measures to avoid both hyperglycemia and hypoglycemia in neurocritical care patients are essential.

Studies conducted that have evaluated IIT in neurocritical care patients have not shown differences in mortality or functional outcome when tight glucose control is used.^{29-32,73-75} Some of these studies have shown lower infection rates in neurocritical care patients but increased risk of hypoglycemic episodes (serum glucose < 50-80 mg/dL).²⁹⁻³¹ This increased risk of hypoglycemia is of significant concern as evidenced by an observational study of 172 patients following subarachnoid hemorrhage who were treated with an IIT protocol targeting blood glucose between 80 and 110 mg/dL and the adverse effect this complication had on functional outcome.⁷⁶ In this study a blood glucose nadir of < 80 mg/dL was independently associated with higher rates of cerebral infarction, symptomatic cerebral vasospasm, and poor functional outcome.

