for the second consecutive blood glucose value >150 mg/dL but ≤ 300 mg/dL and continue per protocol for a maximum duration of 48 hours. Exenatide will be administered by intravenous infusion (50 ng/min for 30 minutes, then start exenatide infusion 25 ng/min) for the second consecutive blood glucose value >150 mg/dL but ≤ 300 mg/dL and continue per protocol for a maximum duration of 48 hours (dose, route, titration schedule, and duration). Exenatide will be prepared by the Investigational Drug Service. The exenatide infusion initiation and maintenance protocols are outlined in Tables 1&2 of the attached study protocol. The exenatide infusion blood glucose goal will be 110-180 mg/dL. During the exenatide infusion, glucose measurements will be obtained hourly. The exenatide infusion will be temporarily discontinued for blood glucose <110 mg/dL. The exenatide infusion will be restarted once the blood glucose level is at least 110 mg/dL. Episodes of hypoglycemia will be treated according to the following guidelines: 1) glucose <70 mg/dL will be provided 25 mL of dextrose 50% (1/2 amp) 2) blood glucose will be re-checked in 5 minutes; if mental status changes caused by hypoglycemia are not reversed or blood glucose remains <70 mg/dL, the above dextrose administration will be repeated, 3) serum glucose will be checked hourly after dextrose administration and the episode has resolved. Exenatide infusion will be restarted beginning with the second hourly glucose check that is ≥ 110 mg/dL. Insulin sensitive sliding scale using formulary rapid acting insulin will be used for blood glucose 181-300 mg/dL starting at the 2nd hourly glucose check (≥ 2 hours since exenatide initiation). The physician will be notified for any blood glucose >300 mg/dL for initiation of a rescue insulin infusion protocol. All glucose values will be documented in the ICU Electronic Documentation System.

Table 1: Exenatide Infusion Initiation Protocol

Glucose (mg/dL)	Action
151-300	
Give exenatide 50 ng/min for 30 minutes, then start exenatide infusion 25 ng/min
 
Give prokinetic agent per NSICU protocol (reglan, erythromycin, etc)
 
Check glucose hourly
 
Monitor blood pressure continuously during exenatide infusion. If SBP <100 mmHg, contact physician. Decision to discontinue exenatide infusion will be made at the discretion of the treating physician.

Table 2: Exenatide Infusion Maintenance Protocol

Glucose (mg/dL)	Action

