10.1 The following feasibility endpoints are based upon prior literature (Nice-Sugar and Exenatide Study in the Cardiac ICU):

Proportion of patients experiencing severe hypoglycemia (<40 mg/dL), Proportion of patients achieving plasma glucose goal (110-180 mg/dL), Proportion of patients experiencing nausea requiring discontinuation of exenatide therapy

10.2 The following descriptive endpoints are included for describing experience with exenatide use in the NSICU population:

Average blood glucose value during exenatide infusion (48 hours), percent time in glucose range (48 hours), mean time to reach plasma glucose goal (110-180 mg/dL), variability outcome (SD)-MADGE, mean insulin use required (units/kg body weight), proportion of subjects requiring rescue insulin infusion protocol, number of hypoglycemic episodes (<80 mg/dL)/total number of glucose measurements (48 hours), number of subjects with >1 hypoglycemic episode (<80 mg/dL)/total number of subjects (48 hours), correlation of exenatide concentrations with creatinine clearance during infusion, elimination rate constant and area under the concentration-time curve utilizing concentrations after discontinuation of infusion, side effects and adverse events (AEs and SAEs), average daily ICP and CPP during study drug infusion, number of hypotensive episodes (SBP<100 mmHg) (48 hours), number of subjects with >1 hypotensive episode/total number of subjects (48 hours). Other adverse effects will be collected specifically assessing any alterations in gastric motility.

In patients receiving invasive intracranial multimodal monitoring as part of their standard of care, the following endpoints associated with exenatide use will be described:

Percent time outside of range for energy metabolism (glucose <0.7 mmol/L and lactate:pyruvate ratio > 40), glutamate (marker of cerebral ischemia), and glycerol (marker of cell membrane degradation) parameters (48 hours).

Based upon prior literature, the prespecified criteria for determining feasibility include the following: 1) no more than 6 patients (25%) experiencing severe hypoglycemia (<40 mg/dL); 2) at least 18 patients (75%) achieving the plasma glucose goal (110-180 mg/dL); 3) no more than 6 patients (25%) experiencing nausea leading to exenatide discontinuation. These criteria will be utilized to determine whether a future efficacy trial will be pursued.

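### Section 10.2 reports subjects with more than one hypoglycemic or hypotensive episode but not subjects with at least one, and the planned totals generally cannot supply that number

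*Combined protocol and SAP*

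**What the plan says.** For each of two safety events, Section 10.2 (descriptive endpoints) lists one episode summary and one subject-level summary.

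- Glucose below 80 mg/dL: the episode rate "number of hypoglycemic episodes (<80 mg/dL)/total number of glucose measurements (48 hours" and the subject proportion "number of subjects with >1 hypoglycemic episode (<80 mg/dL)/total number of subjects (48 hours".
- Systolic pressure below 100 mmHg: the count "number of hypotensive episodes (SBP<100 mmHg) (48 hours" and the subject proportion "number of subjects with >1 hypotensive episode/total number of subjects (48 hours".

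Section 10.1 has one hypoglycemia proportion that counts any occurrence, at a lower threshold: "Proportion of patients experiencing severe hypoglycemia (<40 mg/dL". Section 10.2 also lists adverse events in general, without a subject-level incidence at either threshold. Section 12 plans rates with 95% confidence intervals for dichotomous outcomes. For these rows the plan does not say what counts as one episode or which glucose source is used.

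**The concern.** A subject whose glucose falls once to, say, 65 mg/dL, or whose systolic pressure falls once below 100 mmHg, enters the episode totals but is in the numerator of no subject-level proportion. The two hypoglycemia proportions are also not nested: one episode at 35 mg/dL counts in the row below 40 but not in the wider row below 80.

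The plan's own rationale points to any occurrence. The background to Specific Aim 3 cites an observational study in which "a blood glucose nadir of < 80 mg/dL was independently associated with higher rates of cerebral infarction". A nadir below a cut is an at-least-one measure. Tables 1 and 2 likewise ask for physician contact at any systolic pressure below 100 mmHg, not only at a recurrence.

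How many subjects had any such event is a basic safety figure for planning a later trial, and the listed endpoints do not give it.

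**Working it through.** The plan gives no figure to reproduce here. The question is whether the listed outputs determine the number of subjects with at least one episode.

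**Inputs.** N = 24 subjects (Section 11). E = total episodes and k = subjects with more than one episode, both planned outputs of Section 10.2. The documents give no episode rate, so the values of E and k below are illustrative. For hypoglycemia, E must first be recovered from the episode rate. That needs the number of glucose measurements to be reported too, because Table 2 adds 5-minute rechecks and a switch to 4-hourly checks, so the number per subject is not fixed.

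**Bounds.** Let s be the number of subjects with exactly one episode. The k subjects with more than one use at least 2k of the E episodes. For k ≥ 1:

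- s lies between 0 and the smaller of N − k and E − 2k;
- the number with at least one, k + s, lies between k and the smaller of N and E − k.

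If k = 0, every episode belongs to a different subject and the number is E. Otherwise the range closes to one value only if E = 2k or k = 24.

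**Examples with N = 24.**

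| E | k | Subjects with >1 | Subjects with ≥1 |
|---|---|---|---|
| 6 | 2 | 2/24 (8.3%) | 2 to 4 |
| 10 | 3 | 3/24 (12.5%) | 3 to 7 |
| 12 | 3 | 3/24 (12.5%) | 3 to 9 |
| 20 | 4 | 4/24 (16.7%) | 4 to 16 |

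**Both ends for E = 10, k = 3.** Three subjects with 4, 3 and 3 episodes give 4 + 3 + 3 = 10, so 3 subjects have at least one. Three subjects with 2 each and four with 1 each give 6 + 4 = 10, so 7 subjects have at least one. The planned episode total and >1 count are the same in both cases. The exact (Clopper-Pearson) 95% limits for x of n are the 2.5% point of Beta(x, n−x+1) and the 97.5% point of Beta(x+1, n−x):

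- 3/24 = 12.5%, 2.7% to 32.4%;
- 7/24 = 29.2%, 12.6% to 51.1%.

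**Dependence on the episode rule.** Take one subject with two consecutive low readings and no others. If each reading is an episode, the subject has two and counts under >1. If a run is one episode, the subject has one and does not count. Under both rules the subject counts under ≥1. For a given glucose source, and without a minimum duration, the at-least-one count does not depend on this choice.

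**The case against.** The strongest reply is that nothing is lost. Glucose and blood pressure are collected throughout, single episodes enter the episode totals, and nothing prevents a ≥1 row from being tabulated later. Adverse event recording also covers part of the ground. Under the Glycemic Control Protocol, "glucose <70 mg/dL will be provided 25 mL of dextrose 50% (1/2 amp", and Section 1.3 (Laboratory Test Abnormalities) captures results that required corrective therapy. It also captures results that interrupted study drug and any result judged clinically significant. Hypotension could be recorded under the general definition in Section 1 or as a significant worsening under Section 1.6. The endpoints are descriptive, in a single-arm study of 24.

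Most of this stands, and it limits the weight of the point. It does not close the gap. Interruption applies to any glucose below 110 mg/dL, so it does not isolate values below 80. Clinical significance is a judgment, and Sections 1 and 1.6 set no pressure threshold. No subject-level adverse event summary by threshold is planned. A row added after the results are seen is also not prespecified.

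A reader might infer that a single value of 70-79 mg/dL can reach the adverse event records only through drug interruption. The clinically-significant item in Section 1.3 contradicts that. A reader might also take >1 either as a deliberate recurrence measure or as a plain slip for ≥1. The documents label it as neither, so the intent has to be asked.

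On glucose source, the background to Specific Aim 1 says of continuous monitoring: "This allows for more intensive monitoring of glycemic variability as well as hyper- and hypoglycemic events". Against that, the Glycemic Variability Protocol assigns the device to variability, and Section 8 reserves the term blood glucose for the arterial measurement. The ambiguity is partly resolved. This and the episode definition are missing detail, not separate faults.

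**Conclusion.** The point holds as a minor gap in descriptive safety reporting. Followed as written, Section 10.2 gives no proportion of subjects with at least one episode below 80 mg/dL or at least one systolic pressure below 100 mmHg, and its other outputs fix that number only if k = 0, E = 2k or k = 24.

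The bounds need no assumed rate. They use N = 24. Section 12 defines the analysis set as everyone consented, so if the denominator is larger, that number replaces 24. The example values of E and k are assumptions.

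Three stronger readings are not supported. First, a reader might infer that single events go unrecorded; the data are collected and the events enter the totals. Second, a reader might want to say how many times larger the ≥1 proportion would be. The documents give neither an episode rate nor a within-subject correlation, and low values trigger treatment, so any such ratio would rest on assumptions alone. Third, a reader might infer that the feasibility decision is affected; its three criteria concern glucose below 40 mg/dL, reaching the glucose goal, and nausea leading to discontinuation, and none uses these rows.

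**What to change.** Confirm whether >1 in the two subject-level rows of Section 10.2 was meant as ≥1. In either case, report the number and proportion of subjects with at least one hypoglycemic episode (below 80 mg/dL) and with at least one hypotensive episode (systolic pressure below 100 mmHg), each with an exact binomial 95% confidence interval. If >1 was intended, keep it as an additional recurrence row.

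State one episode-counting rule for each event and one glucose source, and use them for both the episode summaries and the subject-level rows. The hypoglycemia rate is divided by glucose measurements, which suggests that each low measurement is an episode. If runs of low values are to count once instead, the rate row must follow the same rule.

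The cost is two table rows and a sentence or two of definition, with no new data. The downside is that the safety proportions will look less favourable, and brief single dips will count, particularly with continuously measured blood pressure, unless the investigators' episode definition deals with them.

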2. *To evaluate the pharmacokinetic parameters of exenatide in critically ill patients with acute brain injury.*

Background and Rationale:

Critically ill patients and patients with acute brain injury have been shown to experience a hyperdynamic state resulting in an elevation of creatinine clearance, termed augmented renal clearance (ARC).⁶⁶⁻⁶⁸ Patients with ARC have the potential to eliminate exenatide more quickly than we currently anticipate, as renal clearance is the predominant route of elimination of this drug. This will directly impact the ability to achieve therapeutic drug concentrations with the current recommended dosing regimen.

A recent study by Udy and colleagues evaluated the incidence of ARC in generally critically ill patients throughout their ICU stay.⁶⁶ They found that 65.1% of patients manifested ARC on at least one occasion during the first seven days in the ICU. More specifically, a limited amount of information exists evaluating ARC in patients with acute brain injury. In patients with traumatic brain injury, Udy and colleagues demonstrated an incidence of ARC in 85% of patients with the mean maximum creatinine clearance being 179 mL/min/1.73 m².⁶⁷ In addition, an abstract recently presented at the 2013 Neurocritical Care Annual Meeting utilized vancomycin serum concentrations and determined that patients with aneurysmal subarachnoid hemorrhage also appear to have an increase in renal clearance, with an estimated creatinine clearance of > 140 mL/min.⁶⁸

Our research team has experience in this area as we have also utilized vancomycin serum concentrations to describe drug pharmacokinetics in patients with acute brain injury who underwent thermoregulation.⁶⁹ In patients who underwent controlled normothermia and received vancomycin, we found that the median measured trough concentration and median calculated half-life were significantly lower than predicted values, suggesting that the elevated renal elimination of vancomycin due to ARC outweighs a potential reduction in drug elimination caused by controlled normothermia. This resulted in subtherapeutic vancomycin serum concentrations, which may lead to serious complications.⁶⁹

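### Aim 2 promises the incidence of augmented renal clearance and its effect on exenatide, but section 10.2 has no ARC endpoint or limit, and its one link to renal function is a correlation that does not estimate the loss of exposure

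*Combined protocol and SAP*

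**What the plan says.** The heading of Specific Aim 2 is general: "To evaluate the pharmacokinetic parameters of exenatide in critically ill patients with acute brain injury". Its Background and Rationale goes further. It states that "determining the incidence of ARC in this patient population and its impact on exenatide pharmacokinetic parameters is a critical area for further study", the worry being that exenatide levels may be too low to be therapeutic. Of the paired serum concentrations and urinary creatinine clearances it says: "This will provide a direct representation of the overall renal function along with the incidence of ARC". It adds that renal function can then be compared with exenatide concentrations.

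The same rationale describes ARC only in words, as a raised creatinine clearance. Its figures are results of cited work: an incidence of 65.1% in general ICU patients, 85% in traumatic brain injury with a mean maximum of 179 mL/min/1.73 m², and a subarachnoid haemorrhage abstract "with an estimated creatinine clearance of > 140 mL/min". None is adopted as this study's limit.

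Methodology items 4 and 8 plan exenatide samples at 0, 12, 24, 36 and 48 hours, and one 8-hour urine collection a day for 72 hours, of which 48 are on drug.

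Section 10.2 turns Aim 2 into two descriptive items: the "correlation of exenatide concentrations with creatinine clearance during infusion", and an elimination rate constant and AUC from levels after the infusion stops. Item 12 (Data analysis plan) offers descriptive statistics, with success rates and 95% CIs for dichotomous outcomes. It does not mention ARC or pharmacokinetics.

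**The concern.** The rationale names two quantities: a proportion (how many patients have ARC) and an effect (what ARC does to exenatide). The endpoint list contains no proportion. For the effect it offers only a measure of association whose type is not stated.

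Two things are at stake. First, if incidence is reported with no limit, scale or case rule fixed beforehand, all three can be chosen after the data are seen, and the choice can move the result a long way. Second, the clinical worry behind the aim is about size: how much exposure is lost at high clearance under a fixed infusion rate. A correlation coefficient does not carry that size, and it changes with the spread of clearance among the patients who happen to be enrolled.

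**Working it through.** **No stated figure to reproduce.** The plan gives no expected ARC incidence, expected correlation or precision target. The sample size of 24 completers (item 11) has no statistical inputs. What can be checked is what the listed endpoints could deliver.

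**1. Promise against endpoints.**
- Incidence of ARC: promised in the Aim 2 rationale; absent from 10.1, 10.2 and item 12.
- Numeric ARC limit: none anywhere in the document.
- Impact of ARC on pharmacokinetics: promised in the rationale; 10.2 has the correlation only.
- Elimination rate constant and AUC: listed, but not related to creatinine clearance or ARC.

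**2. How much the limit matters.** Assume, since the documents give no distribution, that clearance is normal with mean 140 and SD 40 mL/min. Incidence = 1 - Φ((limit - mean)/SD).
- Limit 120: 1 - Φ(-0.5) = 69%.
- Limit 160: 1 - Φ(0.5) = 31%.

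At an assumed mean of 179 with the same SD, the figures are 93% and 68%.

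**3. The same r fits very different answers.** Hold r at -0.50. Assume clearance SD 30, a limit of 140 mL/min and a linear relation.

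| Mean clearance | Slope (units per mL/min) | Incidence | Mean difference, ARC minus non-ARC |
|---|---|---|---|
| 100 | -0.3 | 1 - Φ(1.33) = 9% | about -18 units |
| 160 | -0.3 | 1 - Φ(-0.67) = 75% | about -15 units |
| 160 | -1.0 | 75% | about -51 units |

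One value of r is compatible with 9% or 75% incidence and, at 75%, with a difference of 15 or 51 units.

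**4. The same drug effect gives different r.** Assume one relation throughout: nonrenal clearance is 20% of the total at 100 mL/min, mean clearance is 140, and residual SD is 0.3 on the log scale.
- Relative concentration = 1/(0.2 + 0.8 × CL/100).
- Log-log slope at 140 = -(0.8 × 1.4)/(0.2 + 0.8 × 1.4) = -1.12/1.32 = -0.848.
- r ≈ -0.848·s/√((0.848·s)² + 0.3²), where s is the SD of log clearance, about SD/140.
- Clearance SD 15: s = 0.107, r ≈ -0.091/√(0.0083 + 0.09) = -0.29.
- Clearance SD 40: s = 0.286, r ≈ -0.242/√(0.0588 + 0.09) = -0.63.

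Simulating the same relation on the untransformed scale gives about -0.29 and -0.61 to -0.62. So r doubles although the drug behaves identically. The slope stays the same: a 20% higher clearance multiplies concentration by 1.2^(-0.848) = 0.86 in both cases. The exclusion of CrCL below 45 mL/min (Major Exclusion Criteria) also restricts the range on which r depends.

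**5. Precision at n = 24.**
- Exact (Clopper-Pearson) 95% CI for 16/24 = 67%: 44.7% to 84.4%. For 20/24 = 83%: 62.6% to 95.3%.
- Fisher z interval for r = -0.5, one pair per patient: tanh(-0.549 ± 1.96/√21) = -0.75 to -0.12.

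An incidence would be imprecise but reportable, and the correlation already planned is imprecise too.

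**The case against.** **The promise is in the rationale, not the heading, and 10.2 lists genuine pharmacokinetic parameters.** This stands in part. A reader might infer that Aim 2 ends with a single coefficient. It does not: the elimination rate constant and AUC are planned, and AUC measures exposure. But neither is related to renal function, and both call for levels after the infusion stops, while the last scheduled sample falls at its planned end. They do not supply what the rationale says the data will provide.

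**The correlation need not be an untransformed Pearson coefficient.** Correct. The type is not stated, and item 12 allows transformations to reduce asymmetry. The correlation also partly serves the stated comparison of renal function with drug levels. On a log scale, however, it still reports no concentration ratio and still depends on the range of clearance.

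**The cited incidence cannot be matched in three days.** A reader might infer that the plan invites a false comparison with the cited finding that "65.1% of patients manifested ARC on at least one occasion during the first seven days in the ICU". The documents propose no such comparison; the figure is background.

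**The size of the exposure loss might be computed from the cited clearances.** It cannot. The 179 figure is indexed to body surface area and is a mean of maxima, and the documents give neither a reference clearance in these patients nor a nonrenal share.

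**The endpoints are descriptive and the trial is small.** This stands, and it limits the weight of the point.

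**Conclusion.** The concern holds in this form: two quantities named in the Aim 2 rationale have no matching endpoint. ARC incidence has neither an endpoint nor a limit. The effect of renal function on exenatide has only a correlation, which gives direction and strength but not the size of the change in exposure.

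On size, the choice of limit alone could move incidence from 69% to 31%, and r could double with no change in the drug effect. Both illustrations rest on assumed clearance distributions, and the second also on an assumed nonrenal share and residual noise. They show how sensitive the results could be and do not predict what this trial will find. The absence of an ARC endpoint and limit needs no assumption.

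A reader might also infer that the gap weakens the decision on a future efficacy trial. It does not: the criteria in section 10 use only severe hypoglycaemia, attainment of the glucose goal, and nausea leading to discontinuation. This is a change the sponsor should make for Aim 2 to deliver what it describes; it is not a threat to the trial's main conclusion.

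**What to change.** **(a) Add ARC incidence to 10.2.** Report the proportion of treated patients with at least one 8-hour creatinine clearance above one pre-stated ARC limit, on one stated scale, with an exact 95% CI. Give the number of collections per patient. The denominator should be named, because item 12 defines intent-to-treat as everyone consented, and the urine collections are scheduled around the infusion. If the limit is indexed to body surface area, record height and weight; height is not among the listed measurements.

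**(b) Alongside or instead of the correlation, estimate the effect.** Regress log exenatide concentration on log measured creatinine clearance in absolute mL/min, allowing for repeated samples within patient (for example, a random intercept). Use only samples taken after uninterrupted infusion at the maintenance rate, because the protocol pauses and restarts the drug according to glucose, and a sample taken soon after a pause does not reflect the running rate. State how long the uninterrupted period must be and how each sample is paired with a daily urine collection. Report the slope as a concentration ratio for a stated difference in clearance, with its 95% CI.

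**Cost.** This is mainly analysis-plan wording, plus height and weight if the limit is indexed. Concentrations and urine collections are already planned. A limit must be fixed in advance, some samples may be excluded, and the intervals will be wide at n = 24.
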